## 1.12.2. Rationale for main study

Sleep disturbances are a common and often persistent problem following mTBI. Both PTH and sleep disturbances in individuals with mTBI may interact and contribute to poorer outcomes and decreased quality of life [210]. Understanding the factors contributing to these disturbances and identifying effective interventions to ameliorate their impact has the potential to have considerable clinical impact.

# 1.13. Rationale for candidate biological variability study (nested study1)

The vestibular, visual, brain imaging, fluid biomarkers and cerebral physiology workstreams will all be involved in the variability study. This is due to the need to estimate the reliability of the techniques used and allow for this in subsequent use of measurements and interpretation of results. Many measures have not been validated. We will validate the techniques used to establish the variation between participants and the variation within participants. It is important for biomarkers to be reproducible. This will inform the main study, as biomarkers that are not fit for purpose due to excess variability may be dropped from further analyses, as we would suggest the need for refinement of these measurements.

Headache, mental health and the cognition workstreams are not included in the variability study. Headache is assessed utilising clinical history to assign phenotype, diaries to describe a patient's experience of their symptoms and patient reported outcome measures (such as the Headache Impact Test-6, or HIT-6) to describe disability. These are already validated tools (HIT-6) and hence variability does not need assessing [211]. The questionnaires involved in the mental health workstream have also been validated [212-218]. Cognitive outcomes will not be looked at due to test-retest reliability having already been determined by the Department of Brain Sciences at Imperial College London (unpublished data) for the cognitive tests proposed.

# 1.14. Rationale for case-control study (nested study 2)

The case-control study takes patients with mTBI and compares them to healthy controls. This will give us the opportunity to look for biomarkers specific to head injury and the option to perform exploratory work looking at novel biomarkers that can be evaluated in the longitudinal main study.

All workstreams will be looking for TBI-specific biomarkers in addition to the exploratory work.

#### 1.14.1. Rationale for exploratory work within case-control study

The brain imaging workstream will have optional exploratory assessments using optically pumped magnetometer (OPM) and 7T MRI measures. Conventional MEG measures the fields from the brain using superconducting quantum interference devices (SQUIDs). These cryogenically cooled detectors are sufficiently sensitive to measure the extremely small (in the femto-Tesla range) magnetic fields generated by neural current. However, the requirement for cryogenic cooling of superconductors means that detectors must be kept ~2 cm from the head which dramatically lowers sensitivity as the magnetic field decreases with the square of the distance. Furthermore, sensors are fixed in place meaning a one-size-fits-all device in which patients must remain still for long periods of time. This produces an environment often poorly tolerated by patients. However, developments have led to the emergence of new MEG systems built from quantum sensors called OPMs.

These small (Lego-brick sized) devices do not require cryogenic cooling and can be mounted flexibly on the head, adapting to head shape/size, and moving with the subject (thereby negating subject movement). These 'wearable' MEG systems also offer significant improvements in sensitivity and spatial resolution, as well as significant reduction in purchase and running costs. Flexibility means that unlike conventional systems which are large, immovable, and require significant infrastructure, an OPM-MEG could realistically be placed in the back of a vehicle and driven either to specialist centres across the UK, or e.g. to sports grounds where mTBI is commonplace. It is likely that the coming years will see the replacement of conventional cryogenic devices with these new systems. Therefore, another aim of the case-control study will be to record data from patients using a 50 sensor OPM system and compare it to the conventional MEG data.

Brain imaging techniques are constantly evolving and improving. While 3T scanners are now the standard in research centres (and specialised clinical facilities) across the world, 7T UHF scanners are becoming increasingly available. To provide a degree of futureproofing, participants in the casecontrol study will undergo MRI at 7T UHF. UHF MRI can provide additional sensitivity to subtle damage and, in doing so, can help identify markers that could then be assessed at 3T, thus informing the analysis of the data acquired as part of the main protocol. For example, one of the most observed structural abnormalities reported by MRI studies is cerebral microhaemorrhage. This abnormality can be detected using susceptibility weighted imaging (SWI) sequences in MRI but is only successful in a minority of cases at 1/1.5T/3T. However, SWI improves dramatically at 7T UHF MRI, meaning the potential for imaging subtle abnormalities is increased. The potential has been demonstrated for mTBI in a small case study [219] but further investigation is needed. We will therefore acquire multi-echo gradient echo data using the 7T system at the University of Nottingham from which we will be able to derive SWI, QSM and T2\* maps. QSM data will be able to inform us of the venous oxygenation levels which have been shown to be perturbed in TBI [160], providing complementary data to the cerebral physiology assessments (Workstream 8). In the same session, we will acquire other structural scans (MP2RAGE) and investigate whether the enhanced spatial resolution and signal-to-noise ratio provided by 7T can identify additional abnormalities and/or inform the analysis at 3T. In addition, we will explore the benefits of 7T for new biomarkers, namely: image cerebrovasculature to interrogate blood flow across the vascular tree (4D PCA) complementing Workstream 8 – and provide indices of neuroinflammation through magnetisation transfer imaging which may be a useful prognostic biomarker.

# 2. AIMS AND OBJECTIVES

## 2.1. Main study

- To evaluate the accuracy and precision of candidate biomarkers (imaging, clinical, biofluid) in predicting prognosis in mTBI due to impact, blast and sport concussion.
- To identify biomarkers at the time of injury to enable a rapid decision to return to play, work or duty.
- To develop a multifaceted biomarker algorithm to predict prognosis in mTBI.

Biomarkers to be assessed are summarised in Table 2 below, and will include brain imaging (structural, functional, MRI, MEG, EEG), biofluid and hormone biomarkers, visual and vestibular disturbances, cerebral physiology, physical function, mental health, headache markers and cognitive dysfunction.

# **2.2.** Biological variability study (nested study 1)

• To assess the variability of candidate biomarkers in healthy controls and mTBI patients to understand if biomarkers are reliable and that any change in a biomarker indicates change over random fluctuation.

## 2.3. Case-control study (nested study 2)

- To identify novel biomarkers in patients with mTBI compared to healthy controls.
- Exploratory studies will enable mechanistic insights to be gained.

## Table 2: List of primary biomarkers by workstream

Workstream	Assessment	Primary biomarker
Global		
	Return to work/duty/play	Yes/No
	Mayo-Portland adaptability inventory	Score
Headache		
	Headache diary	Monthly headache days
Mental health		
	PCL-5 (Post-Traumatic Stress Disorder checklist for DSM-5)	PTSD (Post-traumatic stress disorder) Yes/No
Vestibular		
	vHIT (video Head Impulse Test)	Functional ability of all six semi- circular canals
Cognition		
	Cognitive battery	corrected Global Composite Score
Visual		
	OCT (Optical coherence tomography)	RNFL thickness (Retinal nerve fibre layer thickness)
Imaging		
	MEG (Magnetoencephalography)	Delta/theta waves
	Structural MRI (Magnetic resonance imaging)	FA (fractional anisotropy) / MD (mean diffusivity)
	Functional MRI	Dynamic connectivity (mean dwell time)
	Physiology fMRI	Cerebrovascular reactivity (CVR)
Fluid / hormone		
	Blood	Glial Fibrillary Acidic Protein
	Blood	Cortisol
Cerebral physiology		
	Doppler	Cerebrovascular reactivity (CVR)
	fNIRS (Functional near infrared spectroscopy)	Neurovascular coupling (relative change in oxy- and deoxyhaemoglobin)
	TMS (Transcranial magnetic stimulation)	Cortical silent period
	EEG (Electroencephalogram)	Delta/theta waves
	Physical function	6-Minute Walk Test
	Exercise capacity	Maximal voluntary contraction / muscular endurance

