## 1.4. Workstream 2, mental health

### 1.4.1. Background

People who have suffered TBI experience higher rates of co-morbid mental health outcomes. In mTBI, 1 in 5 experience mental health disorders at 6 months post injury [62], with a 3-fold increase in the risk of developing a mental illness in the first 6 months post-mTBI [63]. Further, military personnel who experience mTBI are at a significantly increased risk of PTSD, depression and anxiety 3 to 6 months after deployment [64]. PTSD and depression are the most frequent, occurring in up to 50% and 60% of patients respectively [65]. PTSD, as per the Diagnostic and Statistical Manual of Mental Disorders, Fifth Edition (DSM-5) criteria is characterised as exposure to a traumatic event with the presence of intrusion symptoms, avoiding stimuli associated with the event, negative alterations in cognition and mood, and hyper-arousal [66]. We have previously demonstrated several clinical variables that are associated with increased risk of PTSD post-mTBI, including mode of injury (e.g. assault), severity of injury, and pre-existing mental health disorder [67]. Rates of completed suicide are also significant, with the relative risk of suicide post-TBI almost 3 times higher than the general population [68]. Poor mental health contributes uniquely to the burden of living with TBI, with some indication that mental health problems precede functional decline. Hence, better understanding of the aetiology of PTSD and depression post-mTBI could lead to targeted

preventative treatments with significant and wide impact.

Whilst we have previously shown that self-reported outcomes of TBI are more sensitive to patient needs than objective outcome scores [69], the subjective nature of conventional diagnostic methods for PTSD and the high comorbidity of depression mean that an objectively measurable biomarker for diagnosing PTSD would be particularly impactful to clinicians and researchers.

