#### Mental Health:

- PCL-5 (PTSD Checklist for DSM-5) (Primary Measure)
- MINI assessment for DSM-5
- PHQ-9 (Patient Health Questionnaire depression scale)
- GAD-7 (Generalised Anxiety Disorder 7)
- SBQ-R (Suicidal Behaviour Questionnaire-Revised)
- AUDIT (Alcohol Use Disorders Identification Test)

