## 7.8. 3-month assessment – Visits 7-10

If this is their enrolment point into the study, participants will:

- Receive the study actigraphy device and training in how to use it
- Receive training in how to install and use the study app

The study assessments at 3 months will be split into individual days for remote assessments (visit 7 – outlined in 7.6.1), clinical assessments (visit 8 – outlined in 7.6.2, minus hair collection), imaging assessments (visit 9 – outlined in 7.6.3), and exploratory imaging (visit 10 – outlined in 7.6.4).

*Note:* Only those mTBI patients entering the study at 3 months will complete demographic details and physical health components of the clinical assessment visit (as detailed in 7.6.2).

Visit 10 will be discontinued after 50 mTBI patients and 50 healthy controls have completed the visit.

## 7.9. 6-month assessment – Visit 11 & 12

The study assessments at 6 months will be split into individual days for remote assessments (visit 11 – outlined in 7.6.1) and clinical assessments (visit 12 – outlined in 7.6.2) in addition to a short remote interview with a study researcher (*Note: the MINI for DSM-5 will only be performed if the participant registers a score of*  $\geq$  50 *in the* PCL-5). One month prior to the visit day, mTBI patients will be

reminded to wear their actigraph for 2 weeks and asked to complete daily headache and sleep diaries for 28 days, as detailed in 7.6.1. Over this period, participants will also complete weekly mini-cognition battery assessments. The study app will send reminders to complete these assessments.

*Note:* Participants will not complete the medical history components of the clinical assessment visit (as detailed in 7.6.2).

Visit 12 will be discontinued after 100 mTBI patients have completed it.

## 7.10. 12-month assessment – Visits 13

The study assessment at 12 months (visit 13) will consist of remote assessments as per section 7.6.1 in addition to a short remote interview with a study researcher. One month prior to the visit day, participants will be asked to complete daily headache and sleep diaries for 28 days, as detailed in 7.6.1. Over this period, participants will also complete weekly mini-cognition battery assessments. The study app will send reminders to complete these assessments.

## 7.11. 24-month assessment – Visit 14

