### 14.4. Development of a prognostic model

We aim to develop multivariable statistical models that can predict sequelae of mTBI using the investigated biomarkers. The sequelae of mTBI being examined are headache, vestibular dysfunction, mental health (depression, PTSD), cognition, global function and full return to work, play or duty. These clinical outcomes are measured via mean monthly headache days, vestibular disturbance questionnaire, self-reported PHQ-9, self-reported PCL-5, corrected global composite score, and MPAI, respectively. Global composite score and MPAI are continuous outcomes; monthly headache days is a count outcome; and clinical thresholds to PHQ-9 and PCL5 will categorise patients into those with and without depression and PTSD respectively (binary outcomes). Each of these outcomes will be measured at 6-, 12- and 24-months post-injury.

Whilst absolute values of biomarkers will be valuable all biomarkers are measured on multiple occasions, as such characteristics such as the rate of change of biomarkers and time until normalisation will also be considered as potentially important data in their own right.

We aim to recruit 610 participants to follow-up for the prognostic modelling phase of the project. At 6 months, for each of the headache, depression and PTSD outcomes, we will have sufficient sample size to investigate a model with 10 candidate parameters; for the global composite score and MPAI outcomes, we will have sufficient sample size to investigate a model with 44 parameters. Sample size calculations were based on methods proposed by Riley [222, 223]. This will allow for 10% drop out which will be reviewed, and the analysis plan modified accordingly.

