Depending on the type of outcome, various types of statistical modelling approaches will be used. For example, continuous, binary and count outcomes will be modelled using linear, logistic and Poisson regressions respectively. We will build multivariable models that can predict clinical outcomes primarily at 6 months (secondarily, we may investigate outcomes at 12 and 24 months), based on 21-day biomarker data. We will also examine how changes to these biomarkers from 21 days to three months affect the clinical outcome. Models will be developed in line with best practice, using multiple imputation, backwards selection, and multivariable fractional polynomials in the development, as appropriate. We will internally validate the models produced using bootstrapping techniques and allow for optimism by applying a uniform shrinkage factor. Any multivariable models produced will be checked for compliance to model assumptions. Model performance will be assessed in terms of prediction and calibration, for example C-index for the logistic models.

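### PCL-5 is listed as a biomarker only as PTSD yes/no, with no score row, although the full score is collected; used that way as a predictor it loses roughly one third to two thirds of its linear information

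*Protocol*

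**What the plan says.** The list of primary biomarkers at the front of the protocol and Table 2 in section 2 give one mental-health entry, PCL-5, in the form "PTSD (Post-traumatic stress disorder) Yes/No". Appendix 1, headed as the complete list of biomarkers, again has PCL-5 as PTSD yes/no and no row for its score. In the same Appendix 1 block, SOFAS, PHQ-9, GAD-7, SBQ-R and AUDIT are scores, and two MINI rows already give PTSD yes/no.

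The score itself is available. Section 7.6.1 schedules the questionnaire in full at the 21-day remote visit and marks it as the lead mental-health instrument: "PCL-5 (PTSD Checklist for DSM-5) (Primary Measure". Section 7.9 uses a numeric value operationally: "the MINI for DSM-5 will only be performed if the participant" reaches a PCL-5 score of 50 or more.

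Section 14.4 gives PCL-5 a second, separate role as an outcome: "clinical thresholds to PHQ-9 and PCL5 will categorise patients into those with and without depression and PTSD respectively (binary outcomes". The models predict 6-month outcomes "based on 21-day biomarker data". The same section treats the rate of change of biomarkers and the time to normalisation as potentially important data, and plans to examine change between 21 days and three months.

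**The concern.** Cutting a questionnaire score into two groups treats everyone on the same side of the cut as alike. A patient just above it counts the same as one far above it. As an outcome, that may be a deliberate clinical definition. As a predictor, it discards information that has already been collected.

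PCL-5 is the only primary mental-health biomarker, and section 1.4.2 calls PTSD a particularly important outcome. Section 14.3 reduces the candidates by a Delphi process that may draw on case-control results, and section 14.4 then allows backwards selection. At either step, a marker coded in a weak form could look worse than it is.

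The coding also limits the longitudinal use that section 14.4 intends. A large improvement or worsening that does not cross the cut registers as no change. Time to normalisation can be defined only for those who start above it.

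**Working it through.** The protocol states no figure for the information carried by PCL-5 in either form, so there is nothing to reproduce. The check asks how much of a score's linear predictive information survives the cut.

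**Inputs**
- Form of the biomarker: binary (front-matter list, Table 2, Appendix 1).
- Cut-off for the yes/no biomarker: not stated. The value of 50 in section 7.9 only triggers an interview.
- Share positive at 21 days: not stated. Section 1.4.1 offers two loosely related figures. One is "PTSD and depression are the most frequent, occurring in up to 50% and 60% of patients respectively"; the other is one in five with any mental health disorder at 6 months. Neither is PCL-5 positivity at 21 days. **Assumed range: 10% to 50%.**
- Distribution of the score: not stated. **Assumed: normal, or right-skewed (gamma with shape 4, 2 or 1, in order of increasing skew).**

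**Formulas.** For a single predictor with a linear effect, the share of information kept is the squared correlation between the score and its above-cut indicator. Let p be the share positive.
- Normal score: kept = φ(z)² / [p(1−p)], where z is the upper-p point and φ the normal density.
- Gamma score with shape k and cut c: kept = [k·P(G(k+1) > c) − k·p]² / [k·p(1−p)], where G(k+1) is a gamma variable with shape k+1. For k = 1 this reduces to p·(ln p)² / (1−p).

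**Worked cases**
- Normal, p = 0.10: 0.1755² / 0.09 = 0.342 kept, so 66% lost.
- Normal, p = 0.20: 0.2800² / 0.16 = 0.490 kept, so 51% lost.
- Normal, p = 0.50: 0.3989² / 0.25 = 0.637 kept, so 36% lost.
- Gamma shape 1, p = 0.20: 0.20 × 1.6094² / 0.80 = 0.648 kept, so 35% lost.

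**Share of linear information lost**

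| Share positive | Normal | Gamma 4 | Gamma 2 | Gamma 1 |
|---|---|---|---|---|
| 10% | 66% | 52% | 47% | 41% |
| 15% | 57% | 44% | 40% | 37% |
| 20% | 51% | 40% | 37% | 35% |
| 30% | 42% | 36% | 36% | 38% |
| 40% | 38% | 37% | 39% | 44% |
| 50% | 36% | 41% | 45% | 52% |

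The loss runs from about 35% to 66%. Put differently, for this one predictor 100 patients with a 21-day PCL-5 carry the information of roughly 34 to 65. Under a normal score the loss reaches one half only when about 21% or fewer are positive.

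**The case against.** The strongest reply is that the lists do not fix how predictors are coded. Table 2 mixes outcomes with biomarkers: its first row is return to work, duty or play, which is the outcome predicted in the primary analysis. Several other rows match the outcomes in section 14.4, where PCL-5 is deliberately binary. The yes/no entry may therefore name the outcome. This explains Table 2 in part, but not Appendix 1. PHQ-9 is also dichotomised as an outcome in section 14.4, yet Appendix 1 lists it as a score. For PHQ-9 the protocol separates the two roles; for PCL-5 it does not.

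Final coding could be settled in a statistical analysis plan. That is fair, and it is why the loss is stated conditionally. But a complete list of biomarkers that has no PCL-5 score row steers that plan towards the binary form.

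Three stronger readings are tempting, and the protocol does not support them:
- **A contradiction with fractional polynomials.** Section 14.4 foresees "using multiple imputation, backwards selection, and multivariable fractional polynomials in the development, as appropriate". Such terms apply to continuous predictors and can sit beside binary ones, so a yes/no marker does not conflict with the plan.
- **A fixed loss of half or more.** This depends on the share positive and the score's shape, and the protocol gives neither. Most of the cells in the table fall below one half.
- **An effective sample size out of 549** (610 less 10% drop-out). Sections 5.4.1 and 7.1 let patients enter at 3 months, and they have no 21-day PCL-5. The number who will have one is not stated.

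The formula also describes one predictor taken alone. PHQ-9, GAD-7 and the others remain candidates as scores and may carry part of the same information, so the effect on a full multivariable model is not shown. Removal of PCL-5 by backwards selection is a possibility, not a demonstrated result.

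**Conclusion.** The point holds as a defect in the biomarker lists with a conditional cost. All three give PCL-5 only as yes/no, although the full score is collected and neighbouring questionnaires are listed as scores. If that form is used for prediction, about one third to two thirds of the marker's linear information is lost.

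This rests on an assumed 10% to 50% positive, the four score shapes tried, and a linear effect. If risk really stepped up at the cut, the binary form would lose little. No combination in the table falls below about 35%, so the loss is material even where it is well short of half. The inability to register change on one side of the cut needs none of these assumptions. The point concerns the predictor only; the binary PTSD outcome is not in question.

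**What to change.** In the front-matter list, Table 2 and Appendix 1, name the PCL-5 total score, kept continuous, as the mental-health biomarker for predictor use. Keep PTSD yes/no as the binary outcome in section 14.4, and label it as an outcome wherever it stays in the lists.

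No new data, visits or participants are needed. Entered linearly, the score takes one parameter, the same as the yes/no form, so the cost is wording only. A fractional polynomial term would take more than one of the 10 candidate parameters that section 14.4 allows for the headache, depression and PTSD models; that choice should be made within the stated limit.
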